Early Life Interventions for Childhood Growth and Development in Tanzania (ELICIT)

NCT03268902

5 February 2020

Statistical Analysis Plan for Primary and Secondary Outcomes (revised to reflect cognitive SAP)

1. Primary outcome, anthropometry secondary outcomes:

Developed and originally posted to ClinicalTrials.gov 5 February 2020

Page 2

2. Cognitive secondary outcomes:

Developed 13 January 2021; originally posted to ClinicalTrials.gov 27 April 2021

Page 5

I. Unblinding, outcomes, analysis populations, data cleaning

Timing of analysis plan and unblinding

This analysis plan is being posted prior to the termination of data collection (anticipated as early as 24 February, 2020). The study will remain blinded until the following conditions have been reached:

1. All 18-month anthropometry, 18-month cognitive testing, and 18-month questionnaires data collection are completed.
2. Database has been cleaned.
3. Primary analysis has been completed (blinded to intervention group), as described below.

Development of analysis code will be conducted on a dataset in which intervention groups have been randomly permuted. The final primary analysis will be conducted on true intervention groups blinded to which group corresponded to which intervention.

Outcomes

Primary outcome: Length-for-age z-score (LAZ) at 18 months

Secondary outcomes:

1. Weight-for-age z-score (WAZ) at 18 months
2. Head-circumference-for-age z-score (HCZ) at 18 months
3. Weight-for height z-score (WHZ) at 18 months
4. MUAC-for-age z-score at 18 months
5. Mortality
6. SAE's, overall and by category
7. AE's, overall and by category

Analysis populations

1. Intention to Treat (ITT): All children who were enrolled in the study and randomized.
2. Modified Intention to Treat (mITT): All children with a valid 18-month anthropometry measurement. The study was suspended by the Tanzanian regulatory agencies for a 9-week period, requiring some assessments to be performed up to 9 weeks outside the target date; these late measurements of the 18-month anthropometry outcomes related to the study suspension will be included.
3. Per-protocol: All children in the mITT group who met the additional criteria:
 - a. Breastfed (at least partially) through age 6 months
 - b. Received all doses of azithromycin
 - c. Received initial dose of each nitazoxanide course
 - d. Received no more than one drug administration (at 6, 9, 12, and 15 month visits) outside of the 14-day window around the target date

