 - e. Received at least 50% of nicotinamide doses as measured by pill and sachet counting

Cleaning of anthropometry z-score data

Anthropometry z-scores were calculated using the zscorer v0.2 package based on the WHO child growth standards. Growth rates between each pair of adjacent measurements were then calculated. Any growth rates that were in the bottom 0.5% or the top 99.5% of the distribution for each age category were flagged. Absolute Z score differences between each measurement and its two flanking measurements were then used to determine which of the measurements was implausible. This implausible value was then coded as NA. Maternal heights will be cleaned by invalidation of values more than 6 standard deviations from the mean.

II. Analysis of Z-score outcomes (LAZ, WAZ, HCZ, WHZ, MUAC) -- mITT and per-protocol groups

ELICIT is a factorial study assessing two interventions (nicotinamide vs. placebo; antimicrobials vs. placebo). Our a priori plan was to analyze each intervention separately, and the study was powered for each primary effect. Thus, all of the processes described below to compare between intervention groups will first be done for nicotinamide (NIC-A vs. NIC-B)

and then for antimicrobials (ANTI-A vs. ANTI-B). This includes looking for baseline differences and choosing adjustment variables separately between NIC-A vs NIC-B and ANTI-A vs ANTI-B.

To determine if there are any synergistic effects of nicotinamide and antimicrobials, we will then include an interaction term between the two interventions in a linear regression model for the 18-month outcomes. If there is a statistically important interaction (defined as $p < 0.05$ from a Wald test), or a sizeable point estimate of the interaction term (defined as a difference of > 0.2 z-scores), we will report effects separately for NIC alone vs. control, ANTI alone vs. control, and NIC+ANTI vs. control.

Unadjusted analysis: Unadjusted analyses will be conducted by 2-sided t-test with $\alpha = 0.05$ and equal variance.

Adjusted analysis: We will also conduct an adjusted analysis to improve power and/or account for potential baseline differences as well as differences by loss-to-follow-up. Factors considered for the adjusted analysis include:

1. Enrollment measurement of outcome (e.g. LAZ, WAZ, HCZ, MUACZ)
2. Sex
3. Socioeconomic status (measured by the WAMI¹)
4. Maternal age, height, tribe, and education
5. Birth month
6. Hospital birth
7. Firstborn status
8. Ward of residence

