9. Age when 18-month outcome was assessed

A priori, we will include the baseline measure of the corresponding anthropometry outcome in the adjusted analyses (NB: WAZ will be used for MUAC). Each of the remaining covariates above will be assessed in a bivariate analysis for the association with the 18-month outcome using linear regression. Those covariates with $p < 0.2$ or difference of 0.2 z-scores will be included in a multivariable analysis based on a linear regression model including the intervention group and each of the factors meeting the criteria above. For covariates that can be specified in different ways (e.g. using birth month as opposed to birth season), we will choose the model with the highest AIC. If point estimates and/or inference differ substantially between the unadjusted and adjusted analysis, we will rely on the adjusted analysis for the primary interpretation of results to ensure differences at 18-months are not explained by baseline differences.

For baseline characteristics with less than 5% missing data, we will single impute the mean values to retain all children in the adjusted analysis and retain comparability with the unadjusted analysis. In the adjusted analysis, for characteristics with $> 5\%$ missing data, we will consider multiple imputation if the covariate meets the criteria for inclusion in the model. We will also investigate whether missing outcome measurements (or lost-to-follow-up before 18 months) are associated with randomization arm or baseline characteristics. If so, we will use inverse-probability of censoring weighting to account for informative censoring.

Sensitivity analysis for mITT group: Unadjusted and adjusted sensitivity analyses will be performed in which children who have the 18-month outcome measurement taken outside the pre-specified measurement window will be excluded from the mITT group.

II. Adverse events, serious adverse events, and mortality – ITT group

For adverse events and serious adverse events, as well as for specific types of serious adverse events, unadjusted and adjusted incidence rate ratios comparing intervention arms will be calculated using Poisson or negative binomial regression as appropriate, with an offset term for the log of person time at risk.

For the analysis of the effects of antimicrobials, only events and person-time starting at six months (the first scheduled administration of antimicrobials) will be included.

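### The adjusted antimicrobial adverse-event model names no covariates, so the child's pre-treatment event count, a source of extra precision, is not planned for use

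*SAP*

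**What the plan says.** Under Outcomes, the SAP lists SAEs and "AE's, overall and by category" as secondary outcomes. The section on adverse events, serious adverse events and mortality analyses them in the ITT population, defined as "All children who were enrolled in the study and randomized". It says that "unadjusted and adjusted incidence rate ratios comparing intervention arms will be calculated using Poisson or negative binomial regression as appropriate", with log person-time as offset. For antimicrobials, "only events and person-time starting at six months (the first scheduled administration of antimicrobials) will be included".

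That section names no covariate for the adjusted ratio. The nearest list is the nine-item one under Analysis of Z-score outcomes. Its first item is "Enrollment measurement of outcome (e.g. LAZ, WAZ, HCZ, MUACZ"; the others are sex, socioeconomic status, maternal factors, birth month, hospital birth, firstborn status, ward and age at assessment. The list in the cognitive part adds only field worker. Neither contains a count or rate of earlier events.

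For the z-scores the SAP gives its reason for adjusting: "We will also conduct an adjusted analysis to improve power and/or account for potential baseline differences". It also fixes the baseline measure of the corresponding anthropometric outcome in the model in advance.

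**The concern.** The six-month restriction is written only for antimicrobials. This implies that earlier events are recorded and count in the nicotinamide comparison. The per-protocol criteria place drug visits at 6, 9, 12 and 15 months, so events before six months precede scheduled antimicrobial treatment. For this one comparison they are a baseline measure of the outcome itself, the counterpart of enrollment LAZ in the LAZ model.

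By allowing a negative binomial model, the SAP accepts that children may differ in how prone they are to events. The early count measures part of that difference. If it is left out, all of the difference stays in the dispersion term and widens the interval. What is at stake is the precision of a declared harm comparison: a real excess or reduction in AEs under antimicrobials is somewhat harder to see than the recorded data would allow.

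**Working it through.** The SAP states no AE rate, dispersion, sample size or power for these outcomes, so there is no figure to reproduce. All rates, k and rho below are assumptions, shown as ranges.

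**Inputs**
- Outcome window: six months onward (SAP), taken as 12 months, to age 18 months.
- Pre-treatment window: taken as a full six months. The SAP does not give age at enrollment; a shorter window would reduce the gain.
- mu0, mu1: expected events per child in the two windows, so mu0 = rate × 0.5 and mu1 = rate × 1.
- k: between-child variance of the relative event rate.
- rho: correlation between a child's underlying rate before and after six months.

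**Formula.** Without the covariate, the variance of the log rate ratio is proportional to 1/mu1 + k. The best linear predictor from the early count removes D = (rho·k·mu0)² / (mu0 + k·mu0²) from k. The variance ratio is (1/mu1 + k − D) / (1/mu1 + k). The number of children cancels.

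**Numbers, k = 0.5**
- 1 event per year, rho = 1: D = 0.25²/0.625 = 0.100; ratio = 1.400/1.500 = 0.933, a cut of 6.7%.
- 1 per year, rho = 0.5: D = 0.025; ratio = 1.475/1.500 = 0.983, a cut of 1.7%.
- 3 per year, rho = 1: D = 0.75²/2.625 = 0.214; ratio = 0.619/0.833 = 0.743, a cut of 25.7%.
- 3 per year, rho = 0.5: D = 0.0536; a cut of 0.0536/0.833 = 6.4%.
- Any rate, rho = 0: D = 0, no gain.

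Since D is proportional to rho², halving rho quarters the gain. With means of 1 event before and 2 after, the cut is 16.7% at rho = 1 but 4.2% at rho = 0.5.

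**SAE-like rates.** Over k of 0.2 to 1 and rho of 0 to 1, the cut is 0 to 0.4% at 0.1 events per year and 0 to 3.0% at 0.3 per year.

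**Simulation check.** Negative binomial regression was fitted with and without log(early count + 0.5), using lognormal between-child rates, 1,000 children, 300 replicates and a true rate ratio of 0.9.

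| Events/year | k | rho | Variance ratio, simulated | Variance ratio, formula |
|---|---|---|---|---|
| 0.1 | 1 | 1 | 0.99 | 0.996 |
| 1 | 0.5 | 0.5 | 0.99 | 0.983 |
| 1 | 0.5 | 1 | 0.91 | 0.933 |
| 3 | 0.5 | 0.5 | 0.92 | 0.936 |
| 3 | 0.5 | 1 | 0.84 | 0.743 |

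The two agree in pattern. In the most favourable row the simulated gain is smaller: 16% from the spread of the estimates, or 23% from the model standard errors (ratio 0.774), against 26% by formula. The mean log rate ratio moved by 0.002 or less in every setting, so adjustment does not shift the estimate.

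**The case against.** The strongest reply is that nothing here is wrong. Excluding earlier events from the antimicrobial outcome is correct, the planned comparison is unbiased, and its confidence interval already allows for chance imbalance between arms. All of that stands. A reader might infer that the restriction biases the rate ratio or makes it invalid; the SAP gives no support for that.

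A reader might also infer that the plan rules out using the early events. It does not: it is silent on the covariates of the adjusted ratio. The silence still matters, because an adjusted analysis is announced with its content left open, and a covariate chosen after results are seen is not prespecified.

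Three limits on size also stand:
- Gains well above 15% need a child's event rate to persist fully, or nearly so, from the first six months to the following year, or events to be very frequent or very unevenly spread among children. The SAP shows none of these.
- The working compares against a model with no other covariates. If sex, socioeconomic status or ward enters the adjusted model, part of the variation may already be explained. That incremental gain was not computed.
- For SAEs the gain is close to nothing.

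Finally, the SAP implies that early events are recorded but does not say whether they were ascertained in the same way at all ages. Less comparable recording would act like a lower rho.

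**Conclusion.** The point holds as a low-cost gain in precision for AEs overall in the antimicrobial comparison. By its own reasoning for z-scores, the SAP would put the baseline measure of the outcome in the model. Here such a measure is implied to exist, and no use of it is planned.

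Under the assumed inputs (k = 0.5, rho 0.5 to 1, 1 to 3 events per child-year), the variance cut is about 2% to 26%. Interval widths scale with the square root of the ratio, so they narrow by about 1% (√0.983 = 0.991) to 14% (√0.743 = 0.862). The upper end is optimistic in view of the simulation and of any other covariates in the model. At 0.1 to 0.3 events per year the cut is about 0 to 3%, so the case does not extend in substance to SAEs or single SAE categories. The claim is one of lost precision only.

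**What to change.** In the safety section, state the covariates of the adjusted Poisson or negative binomial model. For the antimicrobial comparison of AEs overall, include the child's event count or rate before six months of age, for example log[(events + 0.5)/person-time].

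- Use the same six-month cut-off for the covariate as for the outcome and offset. A covariate window that ran to the first antimicrobial visit would overlap the outcome window for any child seen late, and the SAP expects some visits outside the 14-day window and reports a nine-week suspension.
- Do not use the covariate for nicotinamide, where the SAP implies that these events fall after treatment began.
- For SAEs it is optional, with negligible gain.
- Keep the unadjusted ratio, the six-month outcome restriction and the offset as planned.

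The cost is one derived variable and a line or two of text; on the SAP's implication that early events are recorded, no new data are needed. The wording should be fixed before AE results by arm are seen. If they have been seen already, report the analysis as post hoc.

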Fait accompli: For baseline characteristics with less than 5% missing data, we previously performed single imputation of the mean values to retain all children in the adjusted analysis and retain comparability with the unadjusted analysis. In the adjusted analysis for characteristics with >5% missing data, we will consider multiple imputations if the covariate meets the criteria for inclusion in the model. We will investigate whether missing outcome measurements (or lost-to-follow-up before 18 months) were associated with randomization arm or baseline characteristics. If so, we will use inverse-probability of censoring weighting to account for informative censoring.

Pre specified subgroup analyses for the primary cognitive outcome

We will repeat the analyses above but stratified by these characteristics. Estimates were calculated using the 'contrast' package in R, allowing for the evaluation of possible confounders.

- Sex
- Socioeconomic status (WAMI)
- Maternal education (> 6 years)

- Birth order (first born)
- Low birth weight (<2.5kg)
- Birth season (by month)
